	
 • Fulfilled all eligibility criteria for Study APD811-003 and completed the study as planned • Subjects who discontinued for clinical worsening in Study APD811-003 and were assigned to placebo and completed all End of Study procedures, including RHC, may participate after their data from Study APD811-003 are cleaned and locked 
Key Exclusion Criteria:
 
 • Subjects who enrolled in Study APD811-003 and were withdrawn from study drug treatment due to any AE, serious adverse event (SAE), or clinical worsening if assigned to ralinepag, or subjects who did not complete Study APD811-003 for other reasons. • Female subjects who wish to become pregnant • Systolic blood pressure <90 mmHg at Baseline/Day 1 • Other severe acute or chronic medical or laboratory abnormality that may increase the risk associated with study participation or investigational product administration or may interfere with the interpretation of study results and, in the judgment of the Investigator, would make the subject inappropriate for entry into this study.
Duration per Subject:	Treatment with ralinepag will be indefinite until either marketing approval of ralinepag is granted or the Sponsor discontinues the study. Subjects who remain on ralinepag at study termination and meet all eligibility criteria are eligible to roll into the open-label extension study (ROR-PH-303).
Subject Assignment:	All subjects will receive ralinepag
Sample Size:	Approximately 60 subjects
Primary Outcome Measures:	
The primary endpoint for the study is long-term safety. The safety of ralinepag will be monitored throughout the study with safety endpoints being as follows:
 
 • Treatment-emergent AEs up to 28 days following discontinuation of the study drug. • Treatment-emergent SAEs up to 28 days following discontinuation of the study drug.

Efficacy Assessments:	Efficacy will be assessed via performance of the following procedures: 
 • 6MWT • WHO/NYHA FC assessment • Assessment of clinical worsening • Vital status • RHC
Efficacy Endpoints:	Assessment of time to clinical worsening and change from baseline in Study APD811-003 of the following: 
 • 6MWD • WHO/NYHA FC • Hemodynamics

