6.12.1 Adverse Event Reporting

Subjects will be instructed that they may report AEs at any time. All events reported following study drug administration will be recorded as TEAEs.

Monitoring of AEs will be continued up to 30 days after cessation of study drug administration. In the event that an AE is not resolved or stabilized by this time, the Sponsor in consultation with the Investigator will decide whether to continue to monitor the AE or close-out the event in the database if no further follow-up is necessary.

For this study, an AE is defined as: “Any untoward medical occurrence in a study subject administered any dose of ralinepag and which does not necessarily have to have a causal relationship with this treatment.” An AE can therefore be any unfavorable and unintended sign (including an abnormal laboratory finding), symptom, or disease temporally associated with the use of the study drug, whether or not related to the product.

AEs can be any of the following:

- Unfavorable changes in general condition
- Subjective or objective signs/symptoms
- Concomitant disease or accidents
- Clinically relevant adverse changes in laboratory parameters observed in a subject in the course of a clinical study
- Pre-existing conditions which worsen in severity or frequency or which have new signs/symptoms associated with them

AEs will be elicited at the time indicated in the schedule by asking the question, “Since you were last asked, have you felt unwell or different from usual in any way?” Any adverse or unexpected events, signs, and symptoms will be fully recorded on the AE Form, including details of intensity, onset, duration, outcome, and relationship to the drug as determined by

the Investigator. Whenever possible, a constellation of signs and symptoms should be recorded as a unifying diagnosis (eg, self-limited fever, runny nose, cough, and scratchy throat should be captured as an upper respiratory infection rather than by the individual signs and symptoms). AEs may also be reported at any time. The type and duration of follow-up of subjects after AEs will be documented.

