6.12.2 Serious Adverse Events and Expedited Reporting of Adverse Events

SAEs will be captured from the Study APD811-007 Baseline Visit (Week 25 of Study APD811-003) to 30 days after the last dose of study drug and will be monitored until resolution or stabilization.

An SAE is any untoward medical occurrence that at any dose results in the following outcomes:

- Death
- Is life-threatening
- Required/prolonged hospitalization
- Disability/incapacity
- Congenital anomaly/birth defect
- Important medical event (see below)

An important medical event that may not result in death, be life-threatening, or require hospitalization may be considered an SAE when, based upon appropriate medical judgment, it may jeopardize the subject and may require medical or surgical intervention to prevent 1 of the outcomes listed in this definition. Examples of such a medical event includes allergic bronchospasm requiring intensive treatment in an emergency room or at home, blood dyscrasias, or convulsions that do not result in formal hospitalization.

The following are not considered SAEs despite requiring hospitalization:

- Pre-existing conditions that, in the opinion of the investigator, did not worsen or progress during study participation
- Routinely scheduled procedures or treatment (eg, routine RHC)
- Elective procedures that were scheduled prior to study participation (ie, signing of the informed consent document)

All SAEs, whether or not considered related to study treatment, must be reported to the Sponsor contact within 24 hours of becoming aware of the event. In addition, a completed report using the Sponsor's SAE Report form must be submitted within 24 hours of notification to:

United Therapeutics Global Drug Safety

Global Fax: [REDACTED]

email: [REDACTED]

Other situations as defined in ICH Guideline E2A, *Clinical Safety Data Management: Definitions and Standards for Expedited Reporting* (1994), 21 Code of Federal Regulations Section 312.32, and EU Volume 10 also qualify for expedited reporting. In the following situations, the process will be as detailed for SAEs above:

- SAEs which could be associated with the study procedures
- SAEs and AEs of special interest that could materially influence the benefit-risk assessment of a medicinal product, such as a clinically important increase in the rate of a serious suspected adverse reaction over that listed in the Investigator's Brochure

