11 SAFETY ANALYSES

11.1 ADVERSE EVENTS

AEs are captured from the time the Informed Consent Form is signed. AEs that are ongoing at the parent study Termination Visit are recorded as continuing AEs in the APD811-007 study. All AEs with an onset date on or after the first dose of ralinepag in the APD811-007 study or AEs ongoing from the parent study will be included in data listings and summaries.

The AEs will be coded using the Medical Dictionary for Regulatory Activities, and all summaries will utilize the Preferred Term (PT) and/or System Organ Class (SOC). All AEs and serious adverse events (SAEs) will be organized by treatment group in the parent study and listed by subject number, including onset date (day) and time, stop date (day) and time, verbatim term, corresponding PT and SOC, seriousness, severity, relationship to study drug, action taken with study drug, and outcome.

The overall summary of AEs includes the number of subjects with any AE, the number of subjects with any study drug-related AEs, the number of subjects with AEs leading to study drug withdrawal, the number of subjects with any SAEs, the number of subjects with any severe AEs, and the number of subjects with any study drug-related severe AEs.

The summaries of AEs by SOC and PT will be provided by treatment group in the parent study and overall. The summaries of AEs, SAEs, severe AEs, AEs related to ralinepag, SAEs related to ralinepag, and AEs leading to permanent discontinuation of ralinepag will include the number (percent) of subjects and number of events for each reported PT.

The summary of AEs adjusted for length of ralinepag exposure will include the number (percent) of subjects and number of events for each reported PT, as well as the number of events per patient-years of exposure.

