11.2 DEATHS

All deaths will be listed (including those occurring within 30 days of the last ralinepag dose) by subject number and will include the first ralinepag dose date in Study APD811-007, last ralinepag dose date in Study APD811-007, date of death, and cause of death. The summary of deaths will be presented by the parent study and overall and will include the number (percent) of

subjects who died (including those within 30 days of study participation) and their causes of death.

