12 CHANGES FROM ANALYSIS PLANNED IN THE PROTOCOL

For the final analysis, the following changes have been made to the analyses that are described in the protocol:

- Safety Population will be used for all summaries (protocol Section 9.1 specifies modified Intent-to-Treat Population for efficacy analyses).
- The protocol separated the primary objective and secondary objectives. The analyses will be based on efficacy and safety, not specifically separating the primary and secondary objectives.
- Protocol Section 6.2 states medical and social history would be updated at Baseline in Study APD811-007. These updates were not collected.
- No imputation will be performed for missing efficacy values (protocol Section 9.1 specifies Last Observation Carried Forward imputation for efficacy missing values).
- Baseline for change from baseline in efficacy values will be the APD811-007 baseline value (protocol Section 9.2 specifies the Day 1 pre-dose measurement in Study APD811-003 as the main baseline, with Day 1 of Study APD811-007 as baseline for a secondary analysis).
- Follow-up vital status (mortality) was not collected.
- Local results of BNP/NT-proBNP are not available.

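### The SAP's AE and death summaries do not follow the window in the protocol's primary safety endpoint, SAP 12 does not declare the change, and the percentage who died has no stated limit

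*SAP*

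**What the plan says.** **Endpoint.** The synopsis (Primary Outcome Measures) names two safety endpoints: "Treatment-emergent AEs up to 28 days following discontinuation of the study drug" and "Treatment-emergent SAEs up to 28 days following discontinuation of the study drug".

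**Collection.** Protocol 6.12.1 says "Monitoring of AEs will be continued up to 30 days after cessation of study drug administration". Protocol 6.12.2 captures SAEs from the Baseline Visit "to 30 days after the last dose of study drug and will be monitored until resolution or stabilization". Protocol 6.12.1 also says "All events reported following study drug administration will be recorded as TEAEs", and protocol 8.2.1 likewise defines treatment-emergent by the first dose alone; neither has an upper limit.

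**AE analysis.** SAP 11.1 takes into listings and summaries "All AEs with an onset date on or after the first dose of ralinepag in the APD811-007 study", and in the same sentence adds AEs ongoing from the parent study. It gives no end date. One of its summaries divides events by patient-years of ralinepag exposure.

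**Deaths.** SAP 11.2 lists all deaths and mentions those within 30 days of the last ralinepag dose. The next sentence, for the summary, gives the number and percentage of "subjects who died (including those within 30 days of study participation"), which is a different anchor.

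**Vital status.** Protocol 3.1 and 6.14.1 planned a contact with every subject at study closure. SAP 12 reports: "Follow-up vital status (mortality) was not collected".

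**The concern.** Safety is the primary analysis (protocol 9.2.1), so its tables should be built to the endpoint the protocol names. As written, a programmer following SAP 11.1 would apply neither the 28-day nor the 30-day limit. The same programmer would mix events that began before the first APD811-007 dose into what the protocol calls a treatment-emergent count. A reader of the report could not tell from SAP 12 that this had happened.

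For deaths, a percentage of all treated subjects with no stated window invites reading as mortality over the whole study. Beyond 30 days after last dose, no systematic collection supports that reading. Subjects who leave may differ in risk from those who stay: protocol 6.14 lists clinical worsening and serious or intolerable AEs among the reasons for withdrawal.

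**Working it through.** The plan states no figure to reproduce, so the check is mainly a comparison of the texts.

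| Place | What is counted | Upper limit | Anchor |
|---|---|---|---|
| Synopsis, primary endpoint | Treatment-emergent AEs, SAEs | 28 days | Discontinuation of drug |
| Protocol 6.12.1 and 6.12.2 | AE monitoring, SAE capture | 30 days | Last dose |
| Protocol 6.12.1 and 8.2.1 | Definition of treatment-emergent | None | First dose |
| SAP 11.1 | AEs in listings and summaries | None | First APD811-007 dose, plus AEs ongoing from parent study |
| SAP 11.2, listing | All deaths | None (30 days mentioned) | Last dose |
| SAP 11.2, summary | Number and percentage who died | None (30 days mentioned) | Study participation |

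**1. Is the change declared?** SAP 12 lists seven departures from the protocol. None concerns the AE window or the counting of carried-over AEs.

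**2. Size of 28 versus 30 days.** The share of a subject's AE window lying in days 29 and 30 is 2/(T + 30), with T the days on drug. T is an assumption, because the documents give no exposure.
- 1 year: 2/395.25 = 0.51%
- 2 years: 2/760.5 = 0.26%
- 4 years: 2/1491 = 0.13%

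For about 60 subjects (synopsis), the two days amount to 60 × 2/365.25 = 0.33 person-years.

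**3. Last contact.** The 28-day follow-up has a ±3-day allowance (protocol 6.15), so it falls on days 25 to 31. Some contacts precede both limits. This again concerns only a few days.

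**4. Carried-over AEs.** Protocol 7.2.1.1 has unresolved parent-study AEs carried forward and recorded, so recording them is as planned. Counting them is another matter. They began before the first APD811-007 dose, and for former placebo subjects they began before any ralinepag in either study. They can only add to the counts. In the exposure-adjusted table they also enter the numerator of a rate per year of ralinepag exposure. The documents do not say how many there are.

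**5. Deaths after day 30.** With D subjects off study, constant hazard h and time t from last dose to closure, the expected deaths between day 30 and closure are D × [exp(−h × 30/365.25) − exp(−h × t)]. Protocol 1.1.1 gives background PAH mortality of about 15% in one year, so h = −ln(0.85) = 0.1625 per year. D and t are not in the documents. I assume D from 6 to 30 of 60, and t from 0.5 to 3 years.
- Low end: 6 × (0.98674 − 0.92195) = 0.389 deaths, or 0.6 points of 60.
- High end: 30 × (0.98674 − 0.61413) = 11.18 deaths, or 18.6 points.
- With the 3-year survival range of 35% to 75% from the same section, the ends become 0.23 deaths (0.4 points) and 18.65 deaths (31.1 points).
- If no leaver died after day 30, the figure is zero.

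These are deaths that could occur outside systematic capture, not deaths known to be missing. The spread comes entirely from the assumed inputs, so none of these numbers should be quoted as the size of the problem.

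**The case against.** The SAP's open-ended rule follows the protocol's own definitions of treatment-emergent, which have no end. Collection stops at 30 days, so in practice the data are bounded and the excess over the endpoint is about two days per subject. SAP 11.2 speaks of all deaths, and its parenthesis excludes nothing. The vital-status gap is openly reported in SAP 12, and the planned contact always depended on local rules and on agreement with the subject and investigator. Mortality to closure is not a named endpoint: the synopsis lists vital status among the efficacy assessments, but not among the endpoints.

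Much of this stands, and three stronger readings that a reader might infer are not supported.

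- *The percentage who died is understated.* Not shown. For deaths within 30 days of last dose, SAE capture covers the period and the missing closure contact causes no shortfall by itself. As a measure of mortality to closure, the figure may be low, and this gap cannot make it too high.
- *Later deaths reach the database only by chance.* SAEs that begin within the window are followed to resolution or stabilization (protocol 6.12.2). Subjects who stop for a medical reason stay in the study physician's care until well (protocol 6.14.1). Some later deaths therefore have a planned route in.
- *Events on drug in ROR-PH-303 will enter the tables.* SAP 3 says ongoing subjects are to be combined into that study, so overlap with the post-treatment tail is possible. The documents do not say when dosing there starts or which database records its events.

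What the objection does not answer is that the tables have no stated window, that carried-over AEs are counted, that deaths have two anchors, and that SAP 12 is silent on the AE window.

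**Conclusion.** The SAP's safety tables do not implement the protocol's primary endpoint as written, and the departure is undeclared. The 28-versus-30-day part is minor: at most about 0.5% of the AE window, assuming at least one year on drug. The inclusion of AEs ongoing from the parent study is likely to matter more to the counts, but its size cannot be derived from the documents. The death percentage has no defined window. It may understate mortality to study closure by an amount that the documents do not allow to be computed, since they give no number of leavers, no time off study and no deaths. The conclusion rests on the texts alone and not on the illustrative mortality arithmetic. It should be corrected before the final tables are run.

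**What to change.** 1. In SAP 11.1 and 11.2, use one anchor (last APD811-007 dose) and one window for AE, SAE and death summaries: from the first APD811-007 dose to 30 days after the last, or to the first ROR-PH-303 dose if that is earlier.
2. Tabulate AEs ongoing from the parent study separately. Leave them out of the treatment-emergent counts and the exposure-adjusted rates.
3. Title the death table *on treatment or within 30 days of last dose*. List any later known deaths separately, with a footnote that vital status after that window was not collected.
4. Reconcile the synopsis's 28 days with the 30-day capture, and record the change in SAP 12.

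The cost is SAP wording, a date filter and one extra AE table; no new data are needed, and the timing of the follow-up contact can stay as it is. The downside is that late reported deaths appear in the listing and footnote and not in the headline percentage. That is acceptable because the percentage then covers a period in which deaths were systematically collected.

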6.12.5 Assessment of Adverse Event Relationship to Study Drug

The relationship of an AE to investigational product(s) will be classified using modified WHO criteria (Edwards and Biriell, World Health Organization Collaborating Centre for International Drug Monitoring 1994) as follows.

Related: a clinical event, including laboratory test abnormality, with a reasonable time sequence to administration of the drug, unlikely to be attributed to concurrent disease or other drugs or chemicals, and which follows a clinically reasonable response on withdrawal (dechallenge). Rechallenge information is not required to fulfill this definition; or an event that could also be explained by concurrent disease or other drugs or chemicals where information on drug withdrawal may be lacking or unclear.

Not related: a clinical event, including laboratory test abnormality, with sufficient evidence to accept that there is no causal relationship to drug administration (eg, no temporal relationship to drug administration, because the drug was administered after onset of event; investigation shows that the drug was not administered; proof of other

cause; etc); or an event with a temporal relationship to drug administration which makes a causal relationship improbable, and in which other drugs, chemicals or underlying disease provide plausible explanations.

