7.2 STUDY PROCEDURES

7.2.1 *Baseline Study Procedures – All Subjects*

Subjects who meet all the entry criteria and are eligible for the study will report to the clinical study unit to confirm eligibility for the study and complete all Baseline procedures and receive study drug and instructions. The study drug will be given in the morning at the study site during the Baseline Visit.

7.2.1.1 *Pre-baseline Procedures*

All Week 25 measurements from Study APD811-003 will serve as Baseline assessments for Study APD811-007.

Placebo-treated subjects who discontinued prematurely from Study APD811-003 due to clinical worsening are permitted to enroll in APD811-007 provided that all end of study procedures are performed per the ADP811-003 protocol. For these subjects, the time of the clinical worsening event that led to early termination in Study APD811-003 will serve as the Baseline time point for clinical worsening in APD811-007.

Any unresolved AE from Study APD811-003 will be carried forward and recorded.

7.2.1.2 *Baseline Procedures*

- Medical history (partial history, to update findings from Study APD811-003)
- Physical exam¹
- 12-lead ECG¹
- Clinical laboratory tests (to include hematology, coagulation parameters, serum chemistry, and urinalysis)¹
- Serum pregnancy test (women only)¹
- Vital signs¹
- 6MWT¹
- BNP/NT-proBNP¹
- Assessment of clinical worsening

- WHO/NYHA FC assessment¹
- Record AEs¹
- Record concomitant medications¹

¹ Taken from Week 25 Visit in Study APD811-003

7.2.2 Study Procedures – for Immediate-release Dose Titration Period (Study APD811-003 Placebo Subjects)

Visits after Baseline should occur weekly for each escalation of study drug dose. There should be 1 study visit per week during the Dose Titration Period. Beyond the weekly visit, any additional visit during the Dose Titration Period will be documented as an ‘unscheduled’ visit.

If a subject reaches a stable MTD and no further dose escalations are planned, the Dose Titration Period will be considered completed and will be followed by monthly assessments for the first 3 months and then every 3 months until the subject is discontinued from the study, Sponsor termination of the study, or the last subject enrolled completes approximately 6 months of treatment with ralinepag.

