8.2 DATA CODING

8.2.1 *Adverse Events*

AEs will be coded using the MedDRA and tabulated, including categorical information of interest, such as onset and resolution times, time of onset relative to dose, severity at onset, maximum severity, causal relationship to study drug, and action taken. Whenever possible, a constellation of signs and symptoms should be recorded as a unifying diagnosis (eg, self-limited fever, runny nose, cough, and scratchy throat should be captured as an upper respiratory infection rather than by the individual signs and symptoms). As there is no Screening Period in this study and subjects will enter the study on active treatment, all AEs that occur after the first dose of study drug will be considered treatment emergent.

8.2.2 *Concomitant Medications*

Due to the variability in how medications are recorded, a standard naming convention is required in order to tabulate these data effectively. A common method of standardization is to categorize medications by their Preferred Term. In order to do this, medications will be coded using the WHO Drug Dictionary.

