9.2.1.2 Adverse Events

The AEs will be coded using the most current MedDRA and tabulated, including categorical information of interest, such as onset and resolution times, time of onset relative to dose, severity at onset, maximum severity, causal relationship to study drug, and action taken.

All AEs will be listed by subject and will be summarized and expressed in terms of maximum severity and relationship to study drug.

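### SAP 11.1 mixes AEs carried over from the parent study into every AE summary, so the protocol's treatment-emergent AE endpoint is never tabulated, and SAP 12 does not declare this

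*SAP*

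**What the plan says.** The Protocol Synopsis, under Primary Outcome Measures, names long-term safety as the primary endpoint and lists two measures for it. The first is "Treatment-emergent AEs up to 28 days following discontinuation of the study drug"; the second is the same for SAEs. Protocol 8.2.1 defines the term: "all AEs that occur after the first dose of study drug will be considered treatment emergent".

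Protocol 7.2.1.1 deals with events that start earlier: "Any unresolved AE from Study APD811-003 will be carried forward and recorded". It does not call them treatment-emergent. Protocol 9.2.1.2 is broader: "All AEs will be listed by subject and will be summarized", with no treatment-emergent restriction.

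SAP 2.2 lists the endpoint simply as adverse events. SAP 11.1 then sets one inclusion rule: AEs with onset on or after the first ralinepag dose in APD811-007, "or AEs ongoing from the parent study will be included in data listings and summaries". SAP 13.1 lists nine AE summary tables (14.3.1.1 to 14.3.1.9), including one adjusted for exposure. None is restricted to new-onset events and none is set aside for carried-over events. SAP 12 lists seven departures from the protocol, none of them about AEs.

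**The concern.** The tables that should carry the primary safety result count a different set of events from the one the protocol names.

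- **Former placebo subjects.** An AE ongoing at entry began before any ralinepag, yet it is counted in the ralinepag extension tables.
- **Former ralinepag subjects.** The event began on ralinepag but in APD811-003, outside the extension's exposure period. The problem is timing rather than attribution.
- **Exposure-adjusted table.** Events with onset before the APD811-007 clock starts enter the numerator. SAP 9.1 describes both APD811-007 exposure and combined exposure across the two studies, and SAP 11.1 does not say which is the denominator.

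A reader of the report could recover the treatment-emergent figures only by working through the listings. Because SAP 12 is silent, that reader would not know there was a need to.

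A lesser point is that SAP 11.1 gives no post-treatment end to the AE window. The protocol gives 28 days in the Synopsis, but 30 days in section 6.12.1 ("Monitoring of AEs will be continued up to 30 days after cessation of study drug administration") and, for SAEs, in section 6.12.2.

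**Working it through.** **Comparing the texts**

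| Question | Protocol | SAP |
|---|---|---|
| Which AEs form the endpoint? | Treatment-emergent AEs and SAEs (Synopsis) | AEs, unqualified (2.2) |
| What makes an AE eligible? | It occurs after the first dose of study drug (8.2.1) | Onset on or after the first APD811-007 dose, or ongoing from the parent study (11.1) |
| What happens to parent-study AEs? | Carried forward and recorded (7.2.1.1) | Included in the same summaries (11.1) |
| Is there a new-onset-only table? | Needed for the stated measure | None among 14.3.1.1 to 14.3.1.9 (13.1) |
| Is the change declared? | Not applicable | Not among the seven items (12) |

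Each part of the concern follows directly from this comparison.

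**Size**

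The plan states no figure that could be reproduced, and the documents give no AE counts. What follows is illustration on assumed inputs.

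Let c be carried-over AEs per subject, λ new-onset AEs per patient-year, and T mean follow-up in years. All three are assumed. Values of T from 1 to 4 years fit within the 1,793 days (4.9 years) between the original protocol (17 June 2014) and Amendment 4 (15 May 2019), the dates given in the SAP Preface.

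- Rate for new-onset events: λ
- Rate with carried-over events: (λT + c)/T = λ + c/T
- Relative inflation: c/(λT)

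| Case | c | λ | T | Rate, new onset | Rate, with carry-over | Inflation |
|---|---|---|---|---|---|---|
| Low | 0.1 | 4 | 4 | 4.00 | 4 + 0.1/4 = 4.025 | 0.1/16 = 0.6% |
| Middle | 0.5 | 2 | 2 | 2.00 | 2 + 0.5/2 = 2.25 | 0.5/4 = 12.5% |
| High | 2 | 1 | 1 | 1.00 | 1 + 2/1 = 3.00 | 2/1 = 200% |

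The effect falls with longer follow-up. At c = 0.5 and λ = 2 it is 0.5/2 = 25% at 1 year and 0.5/8 = 6.25% at 4 years.

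For the incidence of a single preferred term, a carried-over AE matters only if the subject has no new onset of that term. Each such subject adds 100/n percentage points:

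- Overall column, n about 60 (Protocol Synopsis, Sample Size): 100/60 = 1.7 points. Three such subjects add 5.0 points and six add 10.0.
- Former placebo column, assumed n of 15, 20 or 30: 6.7, 5.0 or 3.3 points per subject.

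With no carried-over cases the change is zero.

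**The case against.** **The protocol is itself inconsistent.** Section 9.2.1.2 has all AEs summarized and 7.2.1.1 has parent-study AEs carried forward, so SAP 11.1 can be read as following those sections. This stands in part: the departure is from the primary outcome measures and the definition in 8.2.1, not from the AE analysis paragraph. Neither section, however, makes an AE that began before dosing treatment-emergent.

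**Treatment emergence could be read more widely.** Protocol 6.12.1 also classes events reported after study drug administration as treatment-emergent, and first dose could mean first ralinepag in either study. The reporting wording does not reach AEs carried in at Baseline. The first-ralinepag reading could cover former ralinepag subjects, but on no reading does it cover AEs that began on placebo.

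**The direction might reverse for rates.** Take the middle case for former ralinepag subjects and use combined exposure, adding 25 weeks (0.48 years) of APD811-003. The rate is then 4.5/2.48 = 1.81, below 2.00. This compares rates with different denominators. Over the same 2.48 years, the APD811-007-onset events alone give 4.0/2.48 = 1.61, so carry-over still raises the rate by 12.5%. The example does show that the denominator must be stated.

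**Related tables are probably protected.** Protocol 6.12.5 gives as an example of not related an event with no temporal relationship, "because the drug was administered after onset of event". That is right: placebo-onset AEs reach the related tables only if a blinded APD811-003 causality judgement is kept unchanged.

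**New-onset events can be recovered.** Listings show onset date and study day, results are split by parent treatment, and the study is descriptive with no formal sample size calculation. All true, and this limits the harm. It also shows how little the correction needs. A primary endpoint should not have to be rebuilt from listings.

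**Conclusion.** The concern holds. Following SAP 11.1 exactly, none of the nine AE summary tables reports treatment-emergent AEs as the protocol defines them, and SAP 12 does not say so. For former placebo subjects this is so on every reading of the protocol. For former ralinepag subjects it depends on reading first dose as the first APD811-007 dose, although their carried-over events lie outside the extension's exposure period either way.

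Only the direction is certain: for a fixed denominator, figures that include carried-over events are equal to or higher than treatment-emergent ones. The range of +0.6% to +200% rests wholly on assumed inputs. Nothing in the documents supports the high case in particular, and it should be read as an outer illustration. No hypothesis test depends on these tables, so the consequence is a misdescribed primary safety result rather than a wrong inference. It should be corrected before the final tables are produced.

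**What to change.** In SAP 11.1:

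1. Define a treatment-emergent AE as one with onset, or worsening in severity, on or after the first APD811-007 dose and within one stated post-treatment window. Reconcile the 28 days in the Protocol Synopsis with the 30 days in 6.12.1 and 6.12.2 first.
2. Base the main incidence, severity, relatedness and exposure-adjusted tables on that flag.
3. Add one table of carried-over AEs by parent treatment group.
4. Keep any carried-over AE that leads to permanent discontinuation of ralinepag in the discontinuation table, as a separate labelled row.
5. State that APD811-007 exposure, the first total in SAP 9.1, is the denominator for events with onset in APD811-007.
6. State whether causality of placebo-onset AEs is re-assessed after unblinding.
7. Record the rule in SAP 12.

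The cost is SAP wording, one derived flag and one added table. The onset part of the flag needs only onset dates already collected. The worsening part needs more care. Protocol 6.12.4 records severity at onset and maximum severity but no date of worsening, so it works where the worsening was entered as an AE of its own. Protocol 6.12.1 provides for that by counting as AEs "Pre-existing conditions which worsen in severity or frequency or which have new signs/symptoms associated with them". The SAP should say how worsening without a separate record is handled. The main correction needs no new data collection; a causality re-assessment, if chosen, would be separate work and the correction does not depend on it.
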